3.3 Definition of dose limiting toxicity

Some of the dose limiting toxicity (DLT) and maximum tolerated dose (MTD) definitions are derived from the National Cancer Institute (NCI) Common Terminology Criteria for Adverse Events (CTCAE) Version 4.02. Please note that not all of the events described as DLTs are fully supported by NCI CTCAE but are formed by amalgams of different events in order to assist with assessments of adverse events.

The definition of DLT applies to both the single agent and combination dose escalation arms (Part A of the study [boxes outlined in red in Figure 2]).

A DLT is defined as a highly probably or probably **BI-1206 or rituximab-related AE occurring during** the four weeks of induction treatment and up to one week post the fourth infusion of BI-1206 (i.e. by Day 28/Week 5) which fulfils one or more of the following criteria:

- Neutropenia or neutrophil count decrease Grade 4 ($ANC < 0.5 \times 10^9/L$) for >10 days duration
*see note despite growth factor support
- Febrile neutropenia (fever of unknown origin without clinically or microbiologically documented infection) with Grade 3 or 4 neutropenia (absolute neutrophil count [ANC] $<1.0 \times 10^9/L$) and fever $\geq 38.5^\circ C$).
- Infection (documented clinically or microbiologically) with Grade 3 or 4 neutropenia ($ANC < 1.0 \times 10^9/L$)
- Thrombocytopenia or platelet count decrease Grade 4: a) for ≥ 5 days*see note, or b) associated with active bleeding, or c) requiring platelet infusion
- Grade 3 or 4 non-haematological toxicity. This includes Grade 3 and 4 biochemical AEs as DLTs.

EXCLUDING:

- Grade 3 or 4 nausea or vomiting in patients who have not received optimal treatment with anti-emetics
- Grade 3 or 4 diarrhoea in patients who have not received optimal treatment with anti-diarrhoeals
- Alopecia
- Grade 3 infusion related reactions
- Transient, asymptomatic Grade 3 biochemical abnormalities if agreed by the Sponsor and the study team, including the Chief Investigator
- Event with a fatal outcome.

***Note: In the event of a Grade 4 neutropenia or Grade 4 thrombocytopenia, a full blood count must be performed at least on Day 10 (Day 5 for thrombocytopenia) after the onset of the event to determine if a DLT has occurred. The investigator must continue to monitor the patient closely until resolution to Grade 3 or less. Please See [Section 5.9.4](#) 'Management of thrombocytopenia (Grade 4)' for further details.**

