3.5.3 Single Agent Dose escalation decisions (Part A, Arm 1)

Patients treated during the Part A, Arm 1 dose escalation phase of the trial who either receive four administrations of BI-1206 or experience a DLT will be evaluable for dose escalation and/or cohort expansion decisions in Part A, Arm 1.

Patients who receive less than 80% of their total planned induction doses (total across the four administrations) but complete the DLT period (Week 5) are not evaluable for dose escalation decisions (unless they have experienced a DLT).

Data from all patients who receive less than 4 doses of BI-1206 (single agent) and any available data from Part A, Arm 2 (if opened) will also be reviewed and taken into consideration at dose decision meetings. Data from any other trials investigating BI-1206 will also be considered in the dose escalation decisions.

For patients who do not receive the total full dose, please see [Section 6.2.5.6](#) for decision making on continuation of treatment. [Section 5.9.6](#) 'Dose delays/treatment discontinuation' also offers guidance for re-challenging patients post related AE observation.

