5.9.6 Dose delays and Treatment Discontinuation

In this trial, if a patient experiences one or more of the following toxicities related (highly probably, probably or possibly) to BI-1206 or rituximab treatment, the treatment for that patient should be delayed/modified as described. Please refer to Section 5.9.2 for actions to be taken in event of a reaction during the infusion.

Grade 1 or 2 toxicity (haematological or non-haematological) other than ocular toxicity or infusion related reaction.

No dose modifications or delays are necessary; refer to Section 5.9.3 for guidance on management of ocular toxicity, Section 5.9.2 for guidance on management of infusion related reactions.

Grade 3 or 4 Haematological toxicity that does not meet DLT definition as described in Section 3.3

Treatment with BI-1206 and rituximab, if applicable should be delayed until recovery of the patient's full blood count to Grade ≤ 2 . Treatment may be delayed for a maximum of three weeks. Patients experiencing \geq Grade 3 haematological toxicity lasting longer than three weeks must not receive further treatment with BI-1206 or rituximab. Growth factor support is permissible during this period.

Grade 3 or 4 Non-haematological toxicity that does not meet DLT definition as described in Section 3.3

Refer to Section 5.9.3 for guidance on management of ocular toxicity, Section 5.9.2 for guidance on management of infusion related reactions. For other events, treatment with BI-1206 and rituximab, if applicable, should be delayed until recovery of the AE(s) to Grade ≤ 2 . Treatment may be delayed for a maximum of three weeks. Patients experiencing \geq Grade 3 toxicity lasting longer than three weeks must not receive further treatment with BI-1206 or rituximab.

Please see [Sections 6.2.5.6](#) and [6.2.11.2](#) for further information relating to patient withdrawal from treatment.

Modifications for logistical reasons i.e. Bank Holidays

For logistical reasons (i.e. bank holidays), treatment may be delayed by a maximum of one week or treatment may be given one day earlier (decrease time between dosing to six days during induction therapy) following agreement by CI and Sponsor, prior to commencing treatment.

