5.9.9 Replacement of patients

Patients who come off study due to dose limiting toxicity prior to completing four weeks of induction therapy will not be replaced. Patients who come off study prior to completing four weeks of induction therapy for any other reason will be replaced for purposes of DLT evaluation during the single and combination dose escalation cohorts. Once a RP2D dose has been established (BI-1206 monotherapy and BI-1206 + rituximab combination) patients who withdraw due to disease progression and/or unacceptable toxicity will not be replaced. Other withdrawn patients may be replaced, if considered appropriate, after discussion between the PI, CI and Sponsor.

There may be circumstances based on the emerging data from the trial or IMP availability which result in a patient not being replaced. This will be documented by the Sponsor.

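### Prolonged related cytopenia that ends induction under 5.9.6 is not a DLT, so the patient is replaced and leaves the count that defines the MAD

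*Combined protocol and SAP*

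**What the plan says.** **DLT definition (3.3).** The event must be highly probably or probably related. Uncomplicated neutropenia qualifies only at Grade 4 for more than 10 days, with the words "see note despite growth factor support" attached. Grade 3 neutropenia qualifies only with fever or documented infection. Thrombocytopenia qualifies only at Grade 4, and then only if it lasts at least 5 days, comes with bleeding or needs platelets. No criterion covers haematological toxicity that ends induction.

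**Stopping rule (5.9.6).** One paragraph is headed "Grade 3 or 4 Haematological toxicity that does not meet DLT definition as described in Section 3.3". Treatment waits for recovery to Grade 2 or better, for at most three weeks. Patients with Grade 3 or worse "haematological toxicity lasting longer than three weeks must not receive further treatment with BI-1206 or rituximab". On growth factor: "Growth factor support is permissible during this period".

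**Evaluability (3.5.3; 3.5.4 is parallel for Arm 2).** Patients "who either receive four administrations of BI-1206 or experience a DLT will be evaluable for dose escalation and/or cohort expansion decisions". "Patients who receive less than 80% of their total planned induction doses" are not evaluable unless they had a DLT. Data from patients with fewer than four doses "will also be reviewed and taken into consideration at dose decision meetings".

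**Replacement (5.9.9).** Patients who leave because of a DLT are not replaced. Those who leave before completing induction "for any other reason will be replaced for purposes of DLT evaluation during the single and combination dose escalation cohorts". Section 7.4 ties going off study to no longer continuing treatment. Section 5.9.9 also lets the Sponsor document a decision not to replace a patient.

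**Count (3.4.1, applied to Arm 2 by 3.4.2).** Two DLTs, as defined in 3.3, in up to six patients make the dose the MAD.

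**The concern.** Section 5.9.6 describes a related toxicity severe enough to bar all further dosing and classes it, by its own heading, as not dose-limiting. Evaluability and replacement then remove the patient from the formal count. The loss is not random: the patient is removed because of toxicity. One primary endpoint in each Part A arm is the highest dose with no more than one DLT in up to six patients, so the removal acts directly on the figure that sets the MAD, and always in the direction of escalation. Neutropenia is called unlikely in 2.2.8, but that section lists thrombocytopenia because of data reported in this trial, and prolonged Grade 3 thrombocytopenia follows the same route.

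**Working it through.** **Step 1: dose fraction.** A patient stopped after dose 1, 2 or 3 of 4 has had 25%, 50% or 75% of planned doses. All are below 80% and below four administrations. Without a DLT, the patient is not evaluable.

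**Step 2: direction.** Suppose *n* evaluable patients have *k* DLTs and *s* others were stopped and replaced. As written the rate is *k/n*; with the stops counted it is (*k+s*)/(*n+s*). Since *k* ≤ *n*, the second is never smaller. Example: 1 DLT in 6 with 2 replaced reads 1/6 = 17%, while 3/8 = 37.5% had a DLT or a toxicity stop.

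**Step 3: an example without assumed rates.** Two patients stop after dose 2 with related Grade 3 neutropenia lasting over three weeks and are replaced; three others complete without a DLT. The count is 0 of 3. If the stops counted, the second would be the second DLT and the dose would be the MAD.

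**Step 4: illustration.** The plan states no operating characteristics, so there is no figure to reproduce. Assumptions: DLT rate *p* = 0.10; rate of uncounted toxicity stops *q* = 0.05, 0.10 or 0.20. The per-patient rate is *r* = *p*/(1−*q*) as written, because replaced patients drop out, and *r* = *p*+*q* if counted.

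Three-patient start, escalating on 0 of 3 or 1 of 6:
P = (1−*r*)³ + 3*r*(1−*r*)² × (1−*r*)³.

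At *q* = 0.20:
- As written, *r* = 0.125: 0.670 + 0.192 = 0.862.
- Counted, *r* = 0.30: 0.343 + 0.151 = 0.494.

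One-patient start (allowed for Cohorts 2–4 in Table 1, and for Arm 2 in 5.5). A clean first patient allows escalation. I assume that a toxicity stop expands the cohort to three, that a DLT expands it to six, and that nothing else triggers expansion.
- As written: P = (1−*p*−*q*) + *q* × [three-patient P at *r*] + *p*(1−*r*)⁵. At *q* = 0.20: 0.70 + 0.20 × 0.862 + 0.10 × 0.513 = 0.924.
- Counted: P = (1−*r*) + *r*(1−*r*)⁵. At *q* = 0.20: 0.70 + 0.30 × 0.168 = 0.750.

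| *q* | 3-patient start: as written | counted | gap | 1-patient start: as written | counted | gap |
|---|---|---|---|---|---|---|
| 0.05 | 0.90 | 0.81 | 0.08 | 0.95 | 0.92 | 0.04 |
| 0.10 | 0.89 | 0.71 | 0.18 | 0.94 | 0.87 | 0.08 |
| 0.20 | 0.86 | 0.49 | 0.37 | 0.92 | 0.75 | 0.17 |

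Gaps are taken before rounding. With *p* = 0.05 the three-patient figures are 0.97/0.97/0.96 as written and 0.91/0.81/0.60 counted. Meeting judgement is not modelled.

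**Step 5: timing.** Section 3.3 closes the DLT window at Day 28/Week 5. Grade 3 toxicity first seen on Day 8 reaches three weeks on Day 29, so a criterion that had to be met inside the window would miss many of these stops.

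**The case against.** The strongest reply is that dose decisions are not mechanical. Section 3.4.1 itself allows escalation to stop before two DLTs if higher doses look too toxic. The RP2D is set from toxicity data on all patients entered, not only evaluable ones (3.4.1, 5.6). A dose meeting can choose dose reduction or a halt to recruitment (5.3.2), and 3.3 lets cumulative toxicity weigh in. Clinically relevant related toxicity of Grade 2 or above in a first patient expands the cohort to at least three (5.4.2). The stopped patients stay evaluable for safety (3.5.2) and appear in the adverse-event tables by dose level (13.2). All of this stands. It lets judgement correct the count; it does not put the patient into the count.

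It is also fair that uncomplicated Grade 3 neutropenia need not be a DLT here, since 4.1.1 admits patients with ANC above 0.5 × 10⁹/L when due to lymphoma. The point concerns only related toxicity that ends induction.

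Two stronger readings are tempting. A reader might infer that the protocol forces escalation to an excessive dose. It does not: a meeting decides, and the sentence in 5.4.3 about no DLTs in three patients concerns the format of later cohorts after a one-in-six result. A reader might also infer that Grade 4 neutropenia without growth factor is never a DLT. The note in 3.3 points the other way: the Day 10 blood count determines DLT status and carries no growth-factor condition. That wording is a secondary ambiguity, and the Grade 3 gap exists under either reading.

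**Conclusion.** The gap is real in both Part A arms, but it lies in the formal DLT count. It covers highly probably or probably related, uncomplicated haematological toxicity that arises before dose 4 and stops induction under 5.9.6, chiefly Grade 3 neutropenia or Grade 3 thrombocytopenia lasting more than three weeks. Neutropenia with fever or infection meeting the 3.3 criteria already counts and is unaffected.

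The direction is certain: against counting these stops, the rule can only lower the observed DLT rate. The size is unknown. Under the assumed 10% DLT rate, the gap in escalation probability runs from 0.08 to 0.37 for a three-patient start and from 0.04 to 0.17 for a one-patient start as uncounted stops go from 5% to 20%. No document supports the 20% rate, and for neutropenia alone the low end is more plausible given 2.2.8. These figures should not be read as the expected bias in the final RP2D, because they leave out the discretion to stop early and the review of all patients entered. The point is worth correcting because the correction is cheap, not because the plan as written has been shown to yield a wrong dose.

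**What to change.** 1. **Section 3.3, new criterion:** *Highly probably or probably related haematological toxicity of Grade 3 or above, worse than the patient's baseline grade, with onset in the DLT window, that stops induction under 5.9.6 is a DLT, even if the three-week limit is reached after Day 28/Week 5. The cohort decision waits until the patient's status is known.*
2. **Section 5.9.9:** state that these patients are not replaced.
3. **Section 3.3, first criterion:** write *with or without growth factor support*, in line with the Day 10 note and with growth factor being optional.

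Leave the recovery thresholds in 5.9.4 and 5.9.6 as they are. Relaxing 5.9.6 to recovery to baseline would loosen a stopping rule in a first-in-human trial and conflict with 5.9.4. The worse-than-baseline wording already covers patients who enter with ANC between 0.5 and 1.0 × 10⁹/L due to lymphoma.

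**Cost:** three short clauses and no new visits, samples or data. The DLT definition becomes slightly broader, so escalation may stop at a lower dose, and a cohort decision will occasionally have to wait. Fewer replacement patients would be needed.

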3 TRIAL DESIGN

3.1 Clinical trial objectives and endpoints

3.1.1 Primary objectives and endpoints

Primary objectives	Endpoints
Part A Escalation phase	
Arm 1: To propose a recommended dose for Phase II evaluation of BI-1206 as a single agent in by:	
(a) Establishing the maximum tolerated dose (MTD) or maximum administered dose (MAD) of BI-1206 given once weekly for four weeks, via intravenous infusion in patients with relapsed or refractory B-cell malignancies in Part A only.	(a) Determining the maximal dose (up to 800 mg) of BI-1206 at which no more than one patient out of up to six patients at the same dose level experience a highly probably or probably BI-1206 related dose-limiting toxicity during induction therapy and up to one week post the fourth infusion.
(b) Assessing the safety and toxicity profile of BI-1206 as a single agent in Part A and Part B	(b) Documenting adverse events (AEs), serious adverse events (SAEs) (graded according to NCI-CTCAE Version 4.02) and laboratory parameters and determining their causality in relation to BI-1206. Causality of AEs/SAEs will be assessed by the Investigator.
Arm 2: To propose a recommended dose for Phase II evaluation of BI-1206 in combination with an anti-CD20 antibody by:	
(c) Establishing the MTD or maximum administered dose MAD of BI-1206 and an anti-CD20 antibody given once weekly for four weeks, via intravenous infusion in patients with relapsed or refractory B-cell malignancies in Part A only.	(c) Determining the maximal dose (up to 800 mg) of BI-1206 at which no more than one patient out of up to six patients at the same dose level experience a highly probably or probably BI-1206 or anti-CD20 antibody-related dose-limiting toxicity during induction therapy and up to one week post the fourth infusion.
(d) Assessing the safety and toxicity profile of BI-1206 in combination with an anti-CD20 antibody in Part A and B.	(d) Documenting AEs, SAEs (graded according to NCI-CTCAE Version 4.02) and laboratory parameters and determining their causality in relation to BI-1206 and, where appropriate, anti-CD20 antibody. Causality of AEs/SAEs will be assessed by the Investigator.
Part B Expansion phase	

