3.4 Definition of maximum tolerated dose

3.4.1 Part A, Arm 1:Single-agent dose escalation

If two out of up to six patients at the same dose level experience a DLT as defined in Section 3.3, this dose level of BI-1206 will be considered the maximum administered dose level (MAD) and no further patients will be treated at this dose level. In this case, the maximum tolerated dose (MTD) will be determined as a dose level below the MAD, which could be a dose previously administered or an intermediate dose between a dose already administered and the MAD. This MTD will be agreed following the review of all the relevant toxicity data between the Sponsor and the study team, including the Chief Investigator.

The MAD could also equal the MTD in the event that dose escalation is stopped before two DLTs are observed at a given dose level due to the expectation that higher dose levels would be too toxic to administer to patients, or if the 800 mg dose level is reached.

The RP2D in Part A, Arm 1 which will be used in Part B, Arm 1 of the clinical trial, will be determined by the Sponsor, Chief Investigator and Principal Investigators, following review of all relevant pharmacokinetic/pharmacodynamic (PK/PD) and clinically relevant toxicity data for all patients entered onto the trial in Part A Arm 1, and the identified MTD or MAD. All significant toxicities and available data from Part A, Arm 2 and data from any other trials investigating BI-1206 will also be considered in the determination of the RP2D.

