- The decision to expand a minimum of one patient cohort to a 3+3 cohort following a clinically relevant \geq Grade 2 related toxicity will be documented and distributed by the Sponsor to all Investigators as per Section 5.3.4. The decision may occur outside the dose decision meetings as it is dependent on when the event/s occurs. The assessment of a clinically relevant toxicity will end at Week 5 (same as the DLT period i.e. one week post fourth infusion).
- As per Section 9.4, related toxicity will be highly probably, probably and possibly related to BI-1206 (or rituximab in Arm 2).

It should be noted that dose escalation and cohort size decisions will be made based on data from completed cohorts in the single agent arm (Arm 1); available data from the combination arm (Arm 2) will be also be reviewed and considered in the Arm 1 dose decision meetings. Please refer to Section 5.3 for details of the communication plan, the process for dose escalation review and decision making and the dissemination of information.

All patients in a cohort must have completed induction therapy and 7 days post the fourth infusion for dose-escalation to the next cohort to occur. The second patient in any cohort will not commence treatment until after the first patient in that cohort has completed two infusions of BI-1206; the third patient in any cohort will not commence treatment until after the second patient in that cohort has completed one infusion of BI-1206.

Figure 4: Dose escalation decision-making and action if clinically relevant \geq Grade 2 related toxicity and/ or DLT observed at dose levels from Cohort 2 (Part A, Arm 1)

dx = initial dose level dx +1 = 1 level above initial dose

5.4.3 Dose escalation and action if a DLT observed at dose levels from Cohort 2 onwards, Part A, Arm 1

If one instance of DLT is observed in any cohort, the cohort will be expanded to include up to six patients. If one out of the six patients experience a DLT then dose escalation will continue, and the next cohort will consist of a minimum of 3 patients as described in Figure 4. If no DLTs are seen in 3 patients, further escalations will continue as 3+3 cohorts.

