5.5 BI-1206 and rituximab escalation cohorts (Part A, Arm 2)

The combination escalation arm (Part A, Arm 2) will open to recruitment following review of a completed single agent dose level in Arm 1. The starting dose for BI-1206 in combination with rituximab will be agreed at a dose decision meeting based on data from completed cohorts in the single agent arm. The combination dose will not exceed the highest dose of BI-1206 safely given (≤ 1 DLT in up to six patients) as a single agent to date and must be deemed clinically appropriate to combine with rituximab.

The dose(s) of rituximab will be 375 mg/m² based upon the approved dose of rituximab. For the purpose of this trial, all patients including CLL patients will receive 375 mg/m² for every rituximab infusion for consistency.

Once the combination escalation arm (Part A, Arm 2) is opened, it will run in parallel to the single agent escalation arm (Part A, Arm1) but dose decisions and cohort size decisions will be made independently for each arm. Combination cohorts will also be a minimum of one patient and dose escalation/cohort expansion decision-making as described in Sections 5.4.2 and 5.4.3 will also apply to the combination escalation cohorts.

It should be noted that dose escalation decisions will be based on data from the combination arm (Arm 2) with available data from the single agent arm (Arm 1) and any other ongoing trials with BI-1206 also being reviewed and considered. Please refer to Section 5.3 for details of the communication plan and process for dose escalation review and dissemination of information.

All patients in a cohort must have completed induction therapy and 7 days post the fourth infusion without DLT for dose-escalation to the next cohort to occur. The second patient in any cohort will not commence treatment until after the first patient in that cohort has completed two infusions of BI-1206 in combination with rituximab; the third patient in any cohort will not commence treatment until after the second patient in that cohort has completed one infusion of BI-1206 and rituximab.

In Part A, Arm 2 the dose level of rituximab will be fixed and the dose level of BI-1206 will be explored in the escalation phase in order to establish the BI-1206 MAD or MTD and RP2D in combination with rituximab, see Section 3.4.

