9.3.2 Serious adverse events

A serious adverse event (SAE) is any AE, regardless of dose, causality or expectedness, that:

- results in death;
- is life-threatening*;
- requires in-patient hospitalisation *or* prolongs existing in-patient hospitalisation (some hospitalisations are exempt from SAE reporting – e.g. hospital admissions planned prior to the patient entering the trial; overnight stays for planned procedures such as blood transfusions (Section 9.7.1);
- results in persistent or significant incapacity or disability;
- is a congenital anomaly or birth defect;
- is any other medically important event.**

*A life-threatening event is defined as an event when the patient was at substantial risk of dying at the time of the adverse event, or use or continued use of the device or other medical product might have resulted in the death of the patient.

**A medically important event is defined as any event that may jeopardise the patient or may require intervention to prevent one of the outcomes listed above. Examples include allergic bronchospasm (a serious problem with breathing) requiring treatment in an emergency room,

serious blood dyscrasias (blood disorders) or seizures/convulsions that do not result in hospitalisation. The development of drug dependence or drug abuse would also be examples of important medical events.

For fatal SAEs, wherever possible report the cause of death as an SAE with a fatal outcome rather than reporting death as the SAE term. When available the autopsy report will be provided to the Sponsor.

If during the course of the study, other medically important events are identified and there is a requirement to report specific events outside of the standard criteria, this will be communicated to site and the protocol will be updated to reflect this.

Any dose limiting toxicity (DLT) must be reported to the CDD Clinical Study Manager (CSM) and CRA within 24 hours of site staff becoming aware of the DLT. The CDD Pharmacovigilance Department must be copied into any initial email notification.

Other reportable events that must be treated as SAEs are listed below.

- Pregnancy exposure to the IMP. Any pregnancy occurring in a patient or a patient's partner during treatment with an IMP or occurring within six months of the last IMP administration, must be reported to the Pharmacovigilance Department in the same timelines as an SAE. These should be reported even if the patient is withdrawn from the trial.

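### Section 3.3 as extracted lists a fatal outcome among the exclusions from dose-limiting toxicity; the line is probably a misplaced criterion, but the wording should be corrected

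*Combined protocol and SAP*

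**What the plan says.** Section 3.3 requires a DLT to be highly probably or probably related to BI-1206 or rituximab, to fall between the start of induction and one week after the fourth infusion, and to meet at least one listed criterion. Four criteria are haematological or concern infection with neutropenia. The fifth reads "Grade 3 or 4 non-haematological toxicity. This includes Grade 3 and 4 biochemical AEs as DLTs". The word EXCLUDING follows, with six bullets: nausea or vomiting without optimal anti-emetics, diarrhoea without optimal treatment, alopecia, Grade 3 infusion reactions, agreed transient asymptomatic Grade 3 biochemical changes, and finally "Event with a fatal outcome".

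The count built on this definition is used in four places:

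- **Primary endpoint, both Part A arms (Section 3.1.1):** the highest dose at which "no more than one patient out of up to six patients at the same dose level experience" a related DLT.
- **Maximum administered dose, MAD (Section 3.4.1, carried to Arm 2 by Section 3.4.2):** "If two out of up to six patients at the same dose level experience a DLT as defined in Section 3.3", that dose is the MAD and no more patients receive it.
- **Expansion and escalation (Section 5.4.3, carried to Arm 2 by Section 5.5):** a first DLT enlarges the cohort to a maximum of six. For a cohort enlarged in this way, the rule on a single DLT is "If one out of the six patients experience a DLT then dose escalation will continue".
- **Arm 2 dose ceiling (Section 5.5):** the combination dose may not exceed the "highest dose of BI-1206 safely given (≤ 1 DLT in up to six patients) as a single agent to date".

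No other readable section says that a related death is a DLT.

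**The concern.** Taken at face value, the definition counts a related Grade 4 non-haematological event but not a related non-haematological death. Two features of the text lead there separately: the fifth criterion stops at Grade 4, and a fatal outcome stands in the list of exclusions.

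This is a first-in-human trial, and the DLT count is its formal stopping rule. A death left out of the count would affect the MAD, the primary endpoint and cohort expansion. Because the Arm 2 ceiling depends on the Arm 1 count, it would also carry into the combination arm. A rule of this kind should have only one possible reading.

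**Working it through.** The documents give no figure to reproduce. The check compares the text with the rules that use it and then counts.

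**1. Two readings of the line**

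- *Flat reading.* The line is the sixth exclusion. A related non-haematological death is not a DLT.
- *Stand-alone reading.* The line is a sixth DLT criterion whose indent has been lost. A related death is a DLT and nothing is miscounted.

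**2. Does an earlier Grade 3 or 4 phase settle it?** On grade alone it could, because Section 3.3 asks only whether the event fulfils a criterion. Against that, Section 9.3.2 asks sites to "wherever possible report the cause of death as an SAE with a fatal outcome rather than reporting death as the SAE term", and Section 9.7 has the worst grade recorded on the SAE form. That would be Grade 5, on the assumption that death is graded 5. These are SAE reporting rules and do not govern DLT adjudication. So the grade gap alone is not decisive; the position of the fatal-outcome line is what could remove such an event from the count.

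**3. Score under each reading.** For one dose level, let k be the number of patients with a counted DLT, and d the number of other patients with a related non-haematological death in the window. The flat score is k, the stand-alone score is k + d, and the MAD threshold is 2 (Section 3.4.1).

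| k | d | Flat score | Stand-alone score | Flat consequence | Stand-alone consequence |
|---|---|---|---|---|---|
| 1 | 1 | 1 | 2 | escalation may continue | MAD |
| 0 | 1 | 0 | 1 | DLT-triggered expansion to six not required | expand to up to six |
| 0 | 2 | 0 | 2 | DLT-triggered expansion to six not required | MAD |

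In the first and third rows the flat score also meets the Arm 2 condition of at most one DLT, while the stand-alone score does not.

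**4. Dose step.** From Cohort 2, Table 1 runs 100, 200, 400, 800 mg: 200/100 = 400/200 = 800/400 = 2. Continuing instead of stopping could expose the next patients to up to twice the dose.

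**5. Evaluability and replacement under the flat reading.** A patient who dies before completing induction could be replaced under Section 5.9.9, since only departure because of a DLT bars replacement. A patient who dies after the fourth dose but inside the window could be counted as evaluable without a DLT (Sections 3.5.3 and 3.5.4).

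**6. Other provisions that bear on a death**

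- Section 3.3: cumulative toxicity is considered for the next dose and the recommended dose.
- Section 3.4.1: escalation may stop before two DLTs.
- Section 5.3.1: dose decisions use safety data from all patients in the cohort.
- Section 5.3.3: the Chief Investigator must agree if absent from the meeting, and the Sponsor's Head of Medical Sciences must approve, before the next patient is recruited.
- Section 5.4.2: clinically relevant related toxicity of Grade 2 or higher in a cohort's first patient, with possibly related events included, expands the cohort to at least three.
- Sections 5.4.2 and 5.5: all patients in a cohort must complete induction plus seven days before escalation.
- Section 5.9.9: replacement may be withheld.
- Section 12: recruitment ceases if treatment is considered too toxic.

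None of these adds a death to the DLT count.

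I give no probability of wrong escalation. It would need a true toxicity rate and a fatal share that the documents do not supply. A standard 3+3 formula would also not describe Cohorts 2 to 4, which may contain one patient.

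**The case against.** The strongest objection is that the problem may not exist in the source document. The extracted text loses list levels elsewhere: the haematology, biochemistry and urinalysis items are flat in Section 7.2 but nested in Section 7.3, and the bone marrow sub-items are flat in Section 7.3 but nested in Section 7.4. In Section 3.3 the other five exclusions all qualify the non-haematological criterion, so they read as its sub-items, yet every bullet appears at one level. A final bullet returning to the outer level would look exactly like this. The content points the same way: a fatal outcome sits oddly beside alopecia and transient laboratory changes, and fits naturally as the criterion above Grade 4. All of this stands, and it makes the stand-alone reading the more likely intent.

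A second objection is that a related death would be discussed and acted on whatever the bullet says. That also stands as far as it goes. The provisions in step 6 make an actual mis-escalation unlikely. They either rest on judgement or operate apart from the DLT count, so they do not repair the definition.

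A reader might go further and infer that the sponsor chose to exempt deaths, or that escalation would proceed after deaths. The documents support neither. No rationale for such an exemption is given, the layout is uncertain, and the reviews can halt or limit escalation. Nor does the point extend to every fatal haematological event: some could still meet the neutropenic infection criterion or the criterion of Grade 4 thrombocytopenia with bleeding, provided the exclusions apply only to the non-haematological criterion.

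**Conclusion.** The point holds as a conditional correction to safety-critical wording. In the extracted text, read literally, a highly probably or probably related non-haematological death in the DLT window scores 0. That can turn a count of 2 into 1 or 0 at the MAD boundary. An actual miscount is not established. If the source shows the line at the outer level, the count is right and only its placement after a list of exclusions is unclear.

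The sizes above are counts under the literal reading and remain subject to intervention by the dose decision meeting. Severity is minor if the line stands alone in the source and should-fix if it does not. Confidence is medium because the original layout could not be seen.

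**What to change.** In Section 3.3:

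1. Add above EXCLUDING, as its own criterion: *any highly probably or probably BI-1206- or rituximab-related event with a fatal outcome (Grade 5) in the DLT window*.
2. Delete the fatal-outcome line below EXCLUDING.
3. State that the exclusions apply only to the Grade 3 or 4 non-haematological criterion.

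This is correct under either layout. Evaluability (Sections 3.5.3 and 3.5.4) and non-replacement (Section 5.9.9) then follow without further edits. The cost is a short wording amendment, with no extra patients, visits or procedures.
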